6.3. EXPOSED SET [ES]

All participants who received a study intervention. Analysis per group is based on the varicella intervention administered.

6.4. PER PROTOCOL SET [PPS]

All eligible participants who received all study interventions as per protocol, were not unblinded, had immunogenicity results post-dose, complied with blood draw intervals (refer to Table 3 of the protocol), without intercurrent medical conditions that may interfere with immunogenicity and without prohibited concomitant medication/vaccination*.

*Intercurrent medical conditions that may lead to elimination from the PPS are defined as confirmed immunodeficiency condition, or development of varicella or herpes zoster in the interval between study intervention administration at Day 1 and the collection of the blood specimen for immunogenicity at Visit 3.

7. GENERAL CONSIDERATIONS

Data will be summarized descriptively (frequency and percentage for categorical data and mean, standard deviation [SD] and range for continuous data, unless specified otherwise). In summary

Document: \\quintiles.net\enterprise\Apps\lasdata\SASb\SAS\GlaxoSmithKline\VNS\217212(VNS 20-006)\Biostatistics\Documentation\SAP\ GSK_217212(VNS 20-006)_ZZA47662_SAP_Final_v7_24Jun2024.docx

Author: PPD Version Number: 7.0
Version Date: 24Jun2024

Template No.: CS_TP_BS016 Revision 6

Reference: CS_WI_BS005

Effective Date: 02Dec2019

tables for categorical data for which categories are defined on the eCRF, all categories will be presented as specified, even if the participant count within that category is zero.

In all the summary tables intervention VV lot 1 and VV lot 2 will be analyzed as pooled lots.

Unless otherwise specified, all data collected during the trial will be presented in listings for the ENR.

7.1. REFERENCE START DATE AND STUDY DAY

Study Day will be calculated from the reference start date and will be used to show start/stop day of assessments and events.

Reference start date is defined as the day of the dose of study vaccination at day 1 and will appear in every listing where an assessment date or event date appears.

If the date of the event is on or after the date of vaccination at Day 1 then:

Study Day = (date of event – date of vaccination at Day 1) + 1.

If the date of the event is prior to the date of vaccination at Day 1 then:

Study Day = (date of event – date of vaccination at Day 1).

In the situation where the event date is partial or missing, Study Day, and any corresponding durations will appear partial or missing in the listings.

7.2. BASELINE

Unless otherwise specified, baseline is defined as the last non-missing measurement taken prior to reference start date (including unscheduled assessments). In the case where the last non-missing measurement and the reference start date coincide, that measurement will be considered pre-baseline.

Document: \\quintiles.net\enterprise\Apps\sasdata\SASb\SAS\GlaxoSmithKline\VNS\217212\VNS 20-006\Biostatistics\Documentation\SAP\ GSK_217212\VNS 20-006_ZZA47662_SAP_Final_v7_24Jun2024.docx

Author: PPD Version Number: 7.0
Version Date: 24Jun2024

Template No.: CS_TP_BS016 Revision 6

Reference: CS_WI_BS005

Effective Date: 02Dec2019

7.3. RETESTS, UNSCHEDULED VISITS AND EARLY TERMINATION DATA

In general, for by-visit summaries, data recorded at the nominal visit will be presented. Unscheduled measurements will not be included in by-visit summaries.

Listings will include all scheduled, and early termination discontinuation data.

7.4. WINDOWING CONVENTIONS

Allowed time window for each visit will be performed as mentioned in “Schedule of Activities”, section 1.3 of protocol.

Intervals between Study Visits

Interval	Planned visit interval	Allowed interval range
Visit 1 → Safety call	1 to 2 days	1 to 3 days
Visit 1 → Visit 2	14 days	14 to 19 days
Visit 1 → Visit 3	42 days	35 to 56 days
Visit 1 → Safety follow-up contact	180 days	180 to 201 days

Document: \\quintiles.net\enterprise\Apps\sasdata\SASb\SAS\GlaxoSmithKline\VNS\217212\VNS 20-006\Biostatistics\Documentation\SAP\ GSK_217212\VNS 20-006_ZZA47662_SAP_Final_v7_24Jun2024.docx

Author: PPD Version Number: 7.0
Version Date: 24Jun2024

Template No.: CS_TP_BS016 Revision 6 Reference: CS_WI_BS005

Effective Date: 02Dec2019

Window convention

Assigned Study Day	Visit label as per protocol	Visit assigned
Day 1	Visit 1	Visit 1 (Day 1)
Day 2 to 3 (Day 1 + 1 to 3 days)	Safety Call	Safety Call (Day 2 – 3)
Day 15 (Day 1 + 14 to 19 days)	Visit 2	Visit 2 (Day 15)
Day 43 (Day 1 + 35 to 56 days)	Visit 3	Visit 3 (Day 43)
Day 181 (Day 1 + 180 to 201 days)	Safety Follow-up contact	Safety Follow-up (Day 181)

7.5. STATISTICAL TESTS

The default significant level will be (5%); 2-sided confidence intervals (CIs) will be 95%, unless otherwise specified in the description of the analyses.

7.6. COMMON CALCULATIONS

Geometric Mean Concentration (GMC):

Distributions of antibodies are generally skewed to the right ([Nauta, 2010](#)). Therefore, prior to any statistical analysis that assumes normally distributed observations, antibody titers or concentrations will be log10-transformed. GMCs and their 95% CI are computed by exponentiating (base 10) the least squares mean and 95% CI of the log10 titers.

The GMC will be calculated using the following formula:

Document: \\quintiles.net\enterprise\Apps\sasdata\SASb\SAS\GlaxoSmithKline\VNS\217212\VNS 20-006\Biostatistics\Documentation\SAP\ GSK_217212\VNS 20-006_ZZA47662_SAP_Final_v7_24Jun2024.docx

Author: PPD Version Number: 7.0
 Version Date: 24Jun2024

Template No.: CS_TP_BS016 Revision 6

Reference: CS_WI_BS005

Effective Date: 02Dec2019

$$10^{\left(\frac{\sum_{i=1}^n \log 10(t_i)}{n}\right)}$$

Where t_1, t_2, \dots, t_n are n observed immunogenicity concentrations.

Concentration below assay cut-off (i.e., <lower limit of quantification or < LLOQ) will be replaced by half the assay cut-off (LLOQ/2) for the purpose of GMC computation.

Seroresponse rate:

Defined as the percentage of participants for whom the post-dose anti-VZV gE antibody concentration (Day 43) is ≥ 300 mIU/mL.

7.7. SOFTWARE VERSION

All analyses will be conducted using SAS version 9.4 or higher.

8. STATISTICAL CONSIDERATIONS

8.1. ADJUSTMENTS FOR COVARIATES AND FACTORS TO BE INCLUDED IN ANALYSES

The following factors will be used in the analyses. For details, refer to section 17.1 and 17.2. The model will include all groups and country as fixed categorical effects in the Analysis of Variance (ANOVA) model.

For the interim analysis an ANCOVA model on log-transformed anti-VZV gE with VNS dose level will be used as covariate in addition to the indicator of investigational vaccine. Likewise, seroresponse will be analyzed using a logistic regression with the same covariate. The dose effect will be constrained to be positive. Country will be included as a fixed effect to both models.

Document: \\quintiles.net\enterprise\Apps\sasdata\SASb\SAS\GlaxoSmithKline\VNS\217212(VNS 20-006)\Biostatistics\Documentation\SAP\ GSK_217212(VNS 20-006)_ZZA47662_SAP_Final_v7_24Jun2024.docx

Author: PPD Version Number: 7.0
Version Date: 24Jun2024

Template No.: CS_TP_BS016 Revision 6

Reference: CS_WI_BS005

Effective Date: 02Dec2019

8.2. MULTICENTER STUDIES

This study will be conducted by multiple investigators at multiple centers. The participants will be randomised to one of the 5 groups (refer to 0 in section 4.1) which will be performed in a 2:2:2:1:1 ratio prior to intervention to provide approximately 200 enrolled participants per each VNS group and 100 enrolled participants per each VV group (VV Lot 1 and VV lot 2).

8.3. MISSING DATA

Missing data (missing, incomplete or partial dates, AE measurement (including missing AE severity and relationship), prior and concomitant medications and death date) will be handled as per APPENDIX 2 of this analysis plan.

Missing immunogenicity data will not be imputed. Concentration below assay cut-off (i.e., lower limit of quantification or < LLOQ) will be replaced by half the assay cut-off (LLOQ/2) for the purpose of GMC computation.

9. OUTPUT PRESENTATIONS

APPENDIX 1 shows conventions for presentation of data in outputs.

The templates provided with this SAP describe the presentations for this study and therefore the format and content of the summary tables, figures, and listings to be provided by IQVIA Biostatistics. Statistical output numbering will follow 'ICH E3 Structure and Content of Clinical Study Reports'.

10. DISPOSITION AND WITHDRAWALS

All participants who are enrolled in the study (those who received a study intervention at Day 1 or were randomized) will be accounted for in this study.

Document: \\quintiles.net\enterprise\Apps\sasdata\SASb\SAS\GlaxoSmithKline\VNS\217212\VNS 20-006\Biostatistics\Documentation\SAP\ GSK_217212\VNS 20-006_ZZA47662_SAP_Final_v7_24Jun2024.docx

Author: PPD Version Number: 7.0
Version Date: 24Jun2024

Template No.: CS_TP_BS016 Revision 6

Reference: CS_WI_BS005

Effective Date: 02Dec2019

10.1. DISPOSITION

Participant disposition, withdrawals, and reasons for exclusion from each analysis set, including inclusion as well as exclusion criteria will be presented for the ENR. Specifically, the number of participants, vaccinated, completed the study, discontinuing the study and the reason for discontinuation will be summarized by study group for the ENR. Additionally, the number of participants returning for each visit for the ES will be presented.

A listing of the disposition for all participants with early withdrawal or discontinuation due to having Coronavirus Disease 2019 (COVID-19) or COVID-19 related issues information will be provided.

10.2. PROTOCOL DEVIATIONS

Protocol deviations (PDs) will be collected in a PD log, as detailed in the Protocol Deviations Management Plan (PDMP). All PDs will be assessed as either important or non-important. PDs will be reviewed by the sponsor, and their status confirmed by the time that all data are cleaned for the Final Analysis. A summary table presenting the number and percentage of participants with important PDs (i.e., those PDs associated to elimination from PPS) will be presented for participants in the ES. A listing of all PDs including an indicator of those excluded from the PPS and an indicator of COVID causality will be provided.

10.2.1. PROTOCOL DEVIATIONS RELATED TO STUDY CONDUCT

A PD is any non-compliance with the clinical trial protocol, GCP, or protocol deviation guidelines requirements. The non-compliance may be either on the part of the participant, the site PI, the study site staff or the sponsor.

10.2.2. PROTOCOL DEVIATIONS RELATED TO IMMUNOGENICITY ANALYSIS

Changes to the procedures or events, which may impact the quality of the immunogenicity data, will be considered significant PDs and will be described within the Clinical Study Report (CSR).

Document: \\quintiles.net\enterprise\Apps\sasdata\SASb\SAS\GlaxoSmithKline\VNS\217212\VNS 20-006\Biostatistics\Documentation\SAP\ GSK_217212\VNS 20-006_ZZA47662_SAP_Final_v7_24Jun2024.docx

Author: PPD Version Number: 7.0
Version Date: 24Jun2024

Template No.: CS_TP_BS016 Revision 6

Reference: CS_WI_BS005

Effective Date: 02Dec2019

This includes any circumstances that could alter the evaluation of the immunogenicity results such as sample processing errors that lead to inaccurate immunogenicity results, and/or inaccurate dosing which could exclude them from the PPS. In addition, participants may also be eliminated from the PPS based on usage of certain concomitant medications or vaccines as described in Section 5.2.2 of the Protocol.

11. DEMOGRAPHIC AND OTHER BASELINE CHARACTERISTICS

Demographic data and other baseline characteristics will be presented for ES and PPS. The following demographic and other baseline characteristics will be reported for this study:

- Age (months) – at the time of first vaccination
- Sex
- Race (as per CDISC categories)
- Ethnicity

Age at time of first vaccination will be derived as the number of complete months between date of birth and date of vaccination. If date of vaccination is missing (the participant was not vaccinated), then date of informed consent will be used.

Descriptive statistics (mean, median, standard deviation and range) will be presented for continuous variables and frequency counts and percentages for categorical variables.

Age category (preterm newborn infants (gestational age < 37 weeks), newborn (0-27 days), infant and toddlers (28 days – 23 months), children (2-11 years), adolescents (12-17 years), adults (18-64 years), 65-84 years and >=85 years) will be summarized by study group where participants are enrolled.

The number of participants enrolled at each country will be summarized by study group.

No statistical testing will be carried out for demographic or other baseline characteristics.

Document: \\quintiles.net\\enterprise\\Apps\\sasdata\\SASb\\SAS\\GlaxoSmithKline\\VNS\\217212\\VNS 20-006\\Biostatistics\\Documentation\\SAP\\GSK_217212\\VNS 20-006\\ZZA47662_SAP_Final_v7_24Jun2024.docx

Author: PPD Version Number: 7.0
Version Date: 24Jun2024

Template No.: CS_TP_BS016 Revision 6

Reference: CS_WI_BS005

Effective Date: 02Dec2019

12. COVID-19 INFECTION ASSESSMENT AND DIAGNOSIS

The COVID-19 infection assessment and diagnosis data including assessment, symptom, diagnosis, visit impact and study impact data will be listed for the ENR and captured on the “COVID-19” page of the eCRF.

13. GENERAL MEDICAL/VACCINATION HISTORY AND EXAMINATIONS

Medical/Vaccination History information will be presented for the ENR.

- Medical History will be coded using Medical Dictionary for Regulatory Activities (MedDRA) central coding dictionary, Version 26.1 or higher.
- Data captured on the “Medical History” page of the eCRF will be presented by System Organ Class (SOC) and Preferred Term (PT). Medical occurrences that begin before the start of study intervention but after obtaining informed consent will be recorded on the Medical History/Current Medical Conditions section of the eCRF, not the AE section.
- Vaccine history will be checked for each participant with the participant’s parent/LAR (protocol-specific vaccines including PCV).

A listing of medical/vaccination history data will be provided.

14. PRIOR, CONCOMITANT AND CO-ADMINISTERED VACCINATIONS

Prior, concomitant and co-administered vaccination will be coded with the current version of the GSK drug dictionary.

- Prior vaccinations are vaccinations per protocol given to participants prior to the dosing of study intervention at Day 1 and are recorded on the eCRF.
- MMR, *Havrix*, and *Prevnar 13* are co-administered with both VNS and VV in this study as

Document: \\quintiles.net\enterprise\Apps\sasdata\SASb\SAS\GlaxoSmithKline\VNS\217212(VNS 20-006)\Biostatistics\Documentation\SAP\ GSK_217212(VNS 20-006)_ZZA47662_SAP_Final_v7_24Jun2024.docx

Author: PPD Version Number: 7.0
Version Date: 24Jun2024

Template No.: CS_TP_BS016 Revision 6

Reference: CS_WI_BS005

Effective Date: 02Dec2019

study interventions.

- Concomitant vaccinations are defined as any vaccine that the participant is receiving as of the time of enrolment or receives during the study (other than study interventions) as recorded on the “Concomitant Vaccination” page of the eCRF.

In addition, if a concomitant vaccination may help explain an AE/SAE, the cause of the AE/SAE or the treatment of an AE/SAE, this information will be recorded under the “Concomitant Medications/Vaccinations Entry” section of the “Expedited Adverse Events (Serious adverse event)” page of the eCRF.

Data will be presented in table summaries for co-administered MMR, *Havrix*, and *Prevnar 13* vaccines, for the ES and in listings for all prior/concomitant and co-administered vaccines.

15. MEDICATIONS

The percentage of participants who started medications after study vaccination will be presented by intervention group for the ES. Medications will be presented by Anatomical Therapeutic Chemical (ATC) classification and preferred drug name and by intervention group.

See APPENDIX 2 for handling of partial dates for medications, in the case where it is not possible to define a medication as prior or concomitant, the medication will be classified by the worst case; i.e., concomitant.

- ‘Prior’ medications are medications which started prior to the dose of study vaccination at Day 1.
- ‘Concomitant’ medications are medications which started on or after the day of the administration of study vaccination at Day 1.

Further details are in Section 6.8 of the Protocol. Concomitant medications which started from Day 1 to Visit 3 blood sample will be presented in table summaries (Any, antipyretic action) and in listings for all medications.

Document: \\quintiles.net\enterprise\Apps\sasdata\SASb\SAS\GlaxoSmithKline\VNS\217212(VNS 20-006)\Biostatistics\Documentation\SAP\ GSK_217212(VNS 20-006)_ZZA47662_SAP_Final_v7_24Jun2024.docx

Author: PPD Version Number: 7.0
Version Date: 24Jun2024

Template No.: CS_TP_BS016 Revision 6 Reference: CS_WI_BS005

Effective Date: 02Dec2019

16. STUDY VACCINATION EXPOSURE

Exposure to study vaccine will be presented for the ES. The date and time of study vaccine administration will be taken from the eCRF “Exposure-VNS vaccine/VV vaccine” form. Similarly, the date and time of co-administered vaccines will be taken from the eCRF “Exposure MMR/Havrix/Prevnar 13” form. For dosing instructions and route, refer to Table 7 of the Protocol amendment 3 dated 18 May 2022.

Data will also be presented in listings.

17. IMMUNOGENICITY OUTCOMES

17.1. PRIMARY IMMUNOGENICITY

17.1.1. PRIMARY IMMUNOGENICITY VARIABLE(S) AND DERIVATION(S)

The primary objective is to evaluate the immune response of VNS vaccine (formulated with different potencies) and VV vaccine in terms of GMC at Day 43. For the derivation of GMC refer to section 7.6.

17.1.2. MISSING DATA METHODS FOR PRIMARY IMMUNOGENICITY VARIABLE

Missing data will not be replaced.

17.1.3. PRIMARY ANALYSIS OF PRIMARY IMMUNOGENICITY VARIABLE

The primary immunogenicity endpoint GMCs of anti-VZV gE antibody concentration at Day 43 will be summarized by vaccine group with their 95% CI derived considering log10-transformed antibody concentrations are normally distributed with unknown variance. Anti-VZV gE antibody concentration will be graphically presented by reverse cumulative curves per vaccine group. The concentration below the assay cut-off will be assigned to half the cut-off for the purpose of GMC

Document: \\quintiles.net\enterprise\Apps\sasdata\SASb\SAS\GlaxoSmithKline\VNS\217212(VNS 20-006)\Biostatistics\Documentation\SAP\ GSK_217212(VNS 20-006)_ZZA47662_SAP_Final_v7_24Jun2024.docx

Author: PPD Version Number: 7.0
Version Date: 24Jun2024

Template No.: CS_TP_BS016 Revision 6

Reference: CS_WI_BS005

Effective Date: 02Dec2019

computation. This will be based on the PPS and the ES. The analysis will also be done split by country.

An adjusted GMC and GMC ratio with 2-sided 95% CI for intervention group which is derived from an ANOVA model on log10 transformed concentration will be tabulated for anti-VZV gE antibody concentration. The model based on the data from all groups will include intervention group as a fixed effect and will be based on the PPS.

The GMC ratio will be estimated along with its corresponding 2-sided 95% CI by exponentiating the least-squares means for the difference.

For the interim analyses, an ANCOVA model on log-transformed anti-VZV gE with VNS dose level will be used as covariate in addition to the indicator of investigational vaccine.

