#### **6.3.2 Randomization to Study Intervention**

The country and center will be used as minimization factors for randomization. Randomization of vaccines will be performed using Interactive Voice Response System (IVRS)/Interactive Web Response System (IWRS). The participants will receive a unique treatment number (refer to [Appendix 1](#) for the definition). Once a treatment number has been assigned, it cannot be re-assigned.

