## 9.0 STATISTICAL CONSIDERATIONS

### 9.1 Statistical Hypotheses

There are no statistical hypotheses in this study. All analyses are descriptive.

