### 9.4.2 Primary Endpoint Analyses

The primary analysis of immunogenicity endpoints will be based on the PPS.

The geometric mean concentrations (GMCs) will be summarized by group with their 95% CI derived considering log-transformed anti-gE antibody concentrations are normally distributed with unknown variance. The concentration below the assay cut-off will be assigned half the cut-off for the purpose of GMC computation.

The group GMC ratio with nominal 95% CI will also be provided. This will be obtained using an analysis of variance (ANOVA) model on log-transformed concentrations. The model based on the data from all groups will include group and country as a fixed effect.

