2.0	28OCT2021	PPD [REDACTED]	
Update following protocol amendment 1 dated 8th October 2021, CBER feedback and to complete the analysis specification:
 
 • Update reference to protocol amendment 1 • New study visit at Day 15 and safety call at Day 2-3 • SRT to be monthly rather than frequently • Update prior medication definition to include all medications started before first dose of study treatment • Ensure consistency on missing data • Varicella-like rash now includes injection site varicella-like rash • Clarified solicited and unsolicited adverse events analysis • Include intensity grades for fever and updated grades for varicella-like rash
3.0	25NOV2021	PPD [REDACTED]	
Update following protocol amendment 2 dated 15th November 2021:
 
 • Include general rash (not varicella-like), drowsiness, irritability and loss of appetite as solicited events

Document: \\quintiles.net\enterprise\Apps\sasdata\SASb\SAS\GlaxoSmithKline\VNS\217212\VNS 20-006\Biostatistics\Documentation\SAP\ GSK_217212\VNS 20-006_ZZA47662_SAP_Final_v7_24Jun2024.docx

Author: PPD Version Number: 7.0
 Version Date: 24Jun2024

Template No.: CS_TP_BS016 Revision 6

Reference: CS_WI_BS005

Effective Date: 02Dec2019

4.0	09JUN2022	PPD	Include countries other than the US. Prevnar 13 not administered in all countries. Include new analysis split by country, duration of solicited events and ongoing solicited events post the solicited period.
5.0	27SEP2022	PPD	Update following the Spanish protocol amendment – adding a co-administered meningococcal vaccine visit at Day 15 for Spain. Update algorithm in appendix 2 to be consistent with section 15.
6.0	04MAR2024	PPD	Reverted update made for the Spanish protocol amendment in SAP version 5. Added derivation for age. Added country as fixed effect to all models. Updated the MedDRA version number and Preferred Terms for Drowsiness and Loss of appetite. Updated Preferred Terms for unsolicited adverse events that are synonymous with solicited adverse events. Added details for handling duplicate solicited adverse events. Explained handling of solicited events recorded beyond the end of the solicited periods. Added definition of immediate unsolicited AEs.
7.0	24JUN2024	PPD	Added Section 18.1.1.1 eCOA Compliance.

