17.2.3. ANALYSIS OF SECONDARY IMMUNOGENICITY VARIABLE

The percentage of participants with a seroresponse will be summarized by intervention groups and corresponding 2-sided 95% exact CI will be reported based on Clopper and Pearson method.

Document: \\quintiles.net\\enterprise\\Apps\\sasdata\\SASb\\SAS\\GlaxoSmithKline\\VNS\\217212\\VNS 20-006\\Biostatistics\\Documentation\\SAP\\GSK_217212\\VNS 20-006\\ZZA47662_SAP_Final_v7_24Jun2024.docx

Author: PPD Version Number: 7.0
Version Date: 24Jun2024

Template No.: CS_TP_BS016 Revision 6

Reference: CS_WI_BS005

Effective Date: 02Dec2019

The analysis will also be done split by country.

The number and percentage of participants with a seroresponse at Day 43 and 2-sided 95% CI on group difference in the seroresponse rate (VV pooled group-VNS group [different potencies – Low, Med, High]) will be computed based on Miettinen and Nurminen method [Miettinen, 1985].

For interim analyses, seroresponse will be analyzed using a logistic regression with VNS dose level used as a covariate. The dose effect will be constrained to be positive.

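### SAP 17.1.3 leaves country out of the ANOVA for the GMC ratio, although Protocol 9.4.2 and SAP 8.1 both require it

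*SAP*

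**What the plan says.** Four places in the current text bear on the model behind the GMC ratio.

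- Protocol 9.4.2, on the ANOVA of log-transformed concentration: "The model based on the data from all groups will include group and country as a fixed effect".
- SAP 8.1: "The model will include all groups and country as fixed categorical effects in the Analysis of Variance (ANOVA) model". The sentence just before it refers to 17.1 and 17.2 for details.
- SAP 17.1.3, the detailed section, which calls its output an adjusted GMC and GMC ratio: "The model based on the data from all groups will include intervention group as a fixed effect and will be based on the PPS".
- SAP 4.3 declares no changes to the analysis from the protocol.

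The SAP version history for v6.0 adds background: "Added country as fixed effect to all models".

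On the interim ANCOVA and logistic models, SAP 8.1 says: "Country will be included as a fixed effect to both models". The matching detailed sentences do not repeat this. The ANCOVA sentence in 17.1.3 names only dose level and the investigational-vaccine indicator, and 17.2.3 reads: "For interim analyses, seroresponse will be analyzed using a logistic regression with VNS dose level used as a covariate".

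On allocation, Protocol 6.3.2 says: "The country and center will be used as minimization factors for randomization".

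**The concern.** The SAP gives two specifications for one model, and the section that should hold the operative detail has the shorter one. A programmer or independent validator working from 17.1.3 would fit group alone and could fairly claim to have followed the SAP. The result would be a between-group estimate and interval for the primary endpoint that differ from those the protocol promises.

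Two features make the omission more than cosmetic. First, with group as the only term, the least-squares mean for a group is its raw mean on the log scale, so the point estimate labelled adjusted is adjusted for nothing. Second, country is one of the two minimisation factors. When allocation is balanced on a factor that predicts the outcome, leaving that factor out keeps its variance in the residual, and the nominal 95% interval is too wide.

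**Working it through.** **Text comparison**

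| Place | Terms named for the GMC-ratio ANOVA |
|---|---|
| Protocol 9.4.2 | group, country |
| SAP 8.1 | group, country |
| SAP 17.1.3 | group |

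All three are current text, so the conflict does not depend on the version history or on SAP 4.3. The by-country split in 17.1.3 is a separate presentation of the group summaries and puts no country term in the pooled ANOVA. The plan states no figure for this model, so there is none to reproduce first.

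**Inputs for the size of the effect**

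- From Protocol 9.2: 200 enrolled per analysis group (VV lots pooled), less 10%, gives 200 × 0.90 = 180 in the PPS. Four analysis groups give N = 4 × 180 = 720.
- Assumed, because the documents give no values: within-country SD 0.4 on the log10 scale; four countries with shares 50/20/20/10%; country explaining a fraction R² of the within-group variance, from 0 to 20%.

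**Interval width under balance within country**

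The half-width on the log10 scale is t × SD × √(2/180), and √(2/180) = 0.1054.

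- With country: residual df 720 − 4 − 3 = 713, t = 1.963. Half-width = 1.963 × 0.4 × 0.1054 = 0.0828. The interval is the ratio divided and multiplied by 10^0.0828 = 1.21.
- Group only: the residual SD becomes 0.4/√(1 − R²), with df 716 and t = 1.963. At R² = 0.20 the SD is 0.447, the half-width is 0.0925, and the factor is 10^0.0925 = 1.24.

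The width ratio, group-only over group plus country, is 1/√(1 − R²). The true variance of the estimated difference is the within-country one, so group-only coverage is about 2Φ(1.96/√(1 − R²)) − 1.

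| R² | Width ratio, formula | Width ratio, simulated (4,000 runs) | Coverage, formula | Coverage, simulated |
|---|---|---|---|---|
| 0 | 1.000 | 1.000 | 0.950 | 0.948 |
| 0.01 | 1.005 | 1.005 | 0.951 | 0.958 |
| 0.05 | 1.026 | 1.026 | 0.956 | 0.959 |
| 0.10 | 1.054 | 1.055 | 0.961 | 0.969 |
| 0.20 | 1.118 | 1.118 | 0.972 | 0.973 |

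The simulated coverages carry a Monte Carlo standard error of about 0.003, and those at R² 0.01 and 0.10 run somewhat high. The formula column is the better guide.

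Fixing the total SD at 0.4 instead of the within-country SD gives the same relative result. At R² = 0.20 the factor falls from 1.210 without country to 1.186 with it, and the half-width ratio is 0.894 = 1/1.118.

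**Shift in the ratio itself**

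Under exact balance within country the two models give the same ratio. With 80 of 800 participants excluded at random, the 95th percentile of the fold difference between the two models' ratios is:

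| R² | Fold difference, 95th percentile |
|---|---|
| 0 | 1.004 |
| 0.05 | 1.015 |
| 0.10 | 1.021 |
| 0.20 | 1.031 |

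As a separate check, a between-country difference of d log10 and a residual imbalance of δ in a country's share shift the ratio by 10^(d × δ). For d = 0.3 and δ = 0.05 this is 10^0.015 = 1.035.

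**The case against.** The best defence is that the intended model can be recovered. SAP 8.1 is the section on factors to include; it states country outright, and the protocol agrees. The 17.1.3 sentence does not say group alone, and the word adjusted implies a further term. On that reading 17.1.3 is incomplete, and 8.1 completes it.

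That establishes intent but does not remove the conflict. SAP 8.1 defers to 17.1 for detail, and what the reader finds there is a complete-looking sentence without country. The output templates mentioned in SAP section 9 might name the terms, but they are not available here and would not correct the SAP text.

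Several limiting points stand:

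- Protocol 9.1 says: "There are no statistical hypotheses in this study. All analyses are descriptive". The group GMCs with their own intervals, which address the primary objective directly, do not use this ANOVA.
- The version history and SAP 4.3 are only supporting evidence. The SAP also adds ES immunogenicity analyses and interim dose-level models that Protocol 9.4 and 9.5 do not describe, so its statement of no changes is weak proof of anything about this model.
- Being a minimisation factor does not settle the matter alone. Center is one too, and neither document puts it in the model. The case for country rests on the protocol and SAP 8.1 having specified it.
- The equality of adjusted and raw GMC holds for the point estimate only. An ANOVA interval pools variance across groups, and a separate group interval need not.
- The two interim sentences are not a contradiction of the same kind, since 8.1 already puts country in both models.

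**Conclusion.** The concern holds. SAP 17.1.3 contradicts Protocol 9.4.2 and SAP 8.1 on the model for the GMC ratio. The likeliest cause is a sentence missed in the v6.0 update, though that is inference. It should be fixed, because the sentence governs the between-group comparison on the primary endpoint.

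Confidence is high on the text and conditional on the size. If country is not prognostic, the choice of model makes essentially no difference. At an R² of 5% the group-only interval is about 2.6% wider. At 20%, an upper value with no anchor in the documents, it is 11.8% wider. The error makes the interval conservative. Any shift in the ratio is small while the groups stay near balance on country. No test, margin, sample size or power statement changes.

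**What to change.** In SAP 17.1.3, reword the ANOVA sentence so that the model has *intervention group and country as fixed effects*, fitted on the PPS. For consistency with 8.1, add country to the interim ANCOVA sentence in 17.1.3 and to the interim logistic regression sentence in 17.2.3. Leave the Miettinen-Nurminen interval as it is; Protocol 9.4.3 and SAP 17.2.3 agree on it.

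The cost is three wording edits. Country is already collected, used in minimisation and specified in 8.1, so the change needs no new data or method and involves no departure from the protocol.
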